3.2.2. Modified Intent-to-Treat Population

The modified intent-to-treat (mITT) population is defined as the all randomized population who took at least 1 dose or part of a dose of study drug and have an evaluable secondary efficacy endpoint. The endpoint is considered as evaluable when both of the following conditions are met:

- Availability of at least 1 measurement value for calculated LDL-C before first dose of study drug (ie, baseline)
- Availability of at least 1 calculated LDL-C value during the efficacy treatment period and within 1 of the analysis windows up to week 96; the efficacy treatment

period is defined as the time from the first double-blind study drug injection up to 21 days after the last double-blind study drug injection

Patients in the mITT population will be analyzed according to the treatment group allocated by randomization.

3.3. The Anti-Drug Antibody Analysis Set

The anti-drug (Praluent) antibody (ADA) analysis will be performed on all treated patients (safety population) with a blood sample at week 0 (baseline) and at least 1 evaluable blood sample for anti-alirocumab antibodies after the first dose of study drug (ADA population).

4. ANALYSIS VARIABLES

4.1. Demographic and Baseline Characteristic Variables

For each patient, demographic and baseline characteristics are obtained from the last available value up to the date and time of the first study treatment administration (i.e. baseline definition). For patients randomized and not treated, the baseline value is defined as the last available value obtained up to the date and time of randomization.

All baseline safety and efficacy parameters (apart from those listed below) are presented along with the summary statistics in the safety and efficacy sections.

The following variables will be summarized:

Demographic Characteristics

- Sex (Male, Female)
- Race (White, Black or African American, Asian, American Indian or Alaska Native, Native Hawaiian or Other Pacific Islander, Other)
- Age in years (quantitative and qualitative variable: <45, ≥ 45 to <65, ≥ 65 to <75, and ≥ 75 years; and <65, and ≥ 65 years)
- Ethnicity (Hispanic or Latino, Not Hispanic or Latino, Unknown)

Baseline Characteristics

- Baseline Weight (kg)
- Baseline Height (cm)
- Baseline Body mass index (BMI) in kg/m² (quantitative and qualitative variable defined as <30, ≥ 30)
- Randomization Strata as Reported in IVRS
- Randomization Strata as Reported from eCRF
- Tobacco Use (current, past, never)
- Alcohol Use (current, past, never)
- LMT at Randomization
- Female Menopausal Status

Baseline Disease Characteristics

- Lipid parameters - quantitative variables for all efficacy parameters
- LDL-C: <70, ≥ 70 to <100, ≥ 100 to <130, ≥ 130 to <160, ≥ 160 to <190, ≥ 190 mg/dL (<1.81, ≥ 1.81 , <2.59, ≥ 2.59 to <3.37, ≥ 3.37 to <4.14, ≥ 4.14 to <4.91, ≥ 4.91 mmol/L)
- HDL-C: <40, ≥ 40 mg/dL (<1.04, ≥ 1.04 mmol/L)
- Fasting TG: <150, ≥ 150 to <200, ≥ 200 mg/dL, and category ≥ 150 mg/dL for mixed dyslipidaemia (<1.7, ≥ 1.7 to <2.3, ≥ 2.3 mmol/L, and category ≥ 1.7 mmol/L),
- Lp(a): <30, ≥ 30 to <50, ≥ 50 mg/dL, and category ≥ 30 mg/dL (<0.3, ≥ 0.3 to <0.5, ≥ 0.5 g/L, and category ≥ 0.3 g/L)
- HbA1c both quantitative variable and qualitative variable defined as: <5.7%, $\geq 5.7\%$ to <6.5%, $\geq 6.5\%$
- hs-CRP
- Hepatitis B surface antigen
- Hepatitis C antibody

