4.2.2. Exclusion Criteria

1. Patients with known Alzheimer's disease or other dementia, schizophrenia, bipolar disorder, severe depression (≥ 11 score of the Geriatric Depression Scale short form [GDS-S; [Appendix 8](#)]), cognitive impairment (<26 score of the Montreal Cognitive Assessment [MoCA]; [Appendix 9](#)]), or patients with a sleep disorder requiring daily pharmacological treatment
2. Patients >85 year old
3. Patient with a hemorrhagic stroke within last 5 years

4. Patients with planned major surgery or carotid stenting
5. Patients who have previously participated in a clinical trial involving a PCSK9 antibody, or had any exposure to a PCSK9 antibody

Note: If patients had previously participated in a clinical trial involving a PCSK9 antibody, and it was subsequently determined that they had been in a placebo group, then this exclusion criterion does not apply.

6. Patients treated with medications listed in [Appendix 3](#), and/or with medications adding up to an anticholinergic burden (ACB) of 3 and above (see [Appendix 4](#)) within 3 months prior to the screening visit

Note: Medications listed in [Appendix 4](#) used “as needed”/pro re nata (PRN), ≤ 2 times per week should not be included in calculating the ACB score.

7. Patients with a history of substance abuse (alcohol or drug) or substance dependence meeting the DSM-IV criteria within 12 months prior to the screening visit ([American Psychiatric Association 2000](#))

8. Signs and symptoms of hyperthyroidism or hypothyroidism (thyroid replacement therapy is permitted, if stable for 12 weeks prior to screening and patient is documented to be euthyroid)

9. History of a myocardial infarction, unstable angina leading to hospitalization, coronary artery bypass graft surgery, percutaneous coronary intervention, uncontrolled cardiac arrhythmia, carotid surgery or stenting, stroke, transient ischemic attack, or carotid revascularization within 3 months prior to the screening visit, or endovascular procedure or surgical intervention for peripheral vascular disease within 3 months prior to the screening visit

10. eGFR <30 mL/min/1.73 m² according to 4-variable Modification of Diet in Renal Disease Study equation (calculated by a central lab).

11. Any condition or situation, including other significant mental or neurological disorders that, in the investigator’s opinion, may confound the study results, or may interfere significantly with the patient’s participation in the study.

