6. STUDY VARIABLES

6.1. Demographic and Baseline Characteristics

Baseline characteristics will include standard demography (eg, age, race, gender, weight, height, etc.), disease characteristics including prior medication history related to LMT, and medical history.

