7.6. Study Procedures

7.6.1. Procedures Performed only at the Screening/Baseline Visit

Medical/surgical history, medication history related to lipid-modifying therapy, demographics, height, hepatitis B surface antigen and hepatitis C antibody testing, HIV testing, serum pregnancy testing, GDS-S and MoCA, and the Motor Screening Task will be performed for the purpose of determining study eligibility or characterizing the baseline population.

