EC	Ethics committee
ECG	Electrocardiogram
EDC	Electronic data capture
eGFR	Estimated Glomerular Filtration Rate
FH	Familial hypercholesterolemia
GCP	Good Clinical Practice
HbA1c	Hemoglobin A1c
HDL	High-density lipoprotein
HDL-C	High-density lipoprotein cholesterol
heFH	Heterozygous familial hypercholesterolemia
HIV	Human immunodeficiency virus
hs-CRP	High-sensitivity C-reactive protein
ICF	Informed consent form
ICH	International Council for Harmonisation
IRB	Institutional Review Board
ITT	Intent-to-treat
IVRS	Interactive voice response system

IWRS	Interactive web response system
LDH	Lactate dehydrogenase
LDL	Low-density lipoprotein
LDL-C	Low-density lipoprotein cholesterol
LMT	Lipid-modifying therapy
LOCF	Last observation carried forward
Lp(a)	Lipoprotein a
MedDRA	Medical Dictionary for Regulatory Activities
mITT	Modified intent-to-treat
MMRM	Mixed-effect model with repeated measures
MoCA	Montreal Cognitive Assessment
MRI	Magnetic resonance imaging
NCEP ATP	National Cholesterol Education Program-Adult Treatment Panel
Non-HDL-C	Non-high-density lipoprotein cholesterol
PAL	Paired Associates Learning
PCSA	Potentially clinically significant abnormal value
PCSK9	Proprotein convertase subtilisin/kexin type 9
PT	Preferred term
Q2W	Every 2 weeks
RBC	Red blood cell
RTI	Reaction Time
SAE	Serious adverse event
SAP	Statistical analysis plan
SAS	Statistical Analysis Software
SC	Subcutaneous
SOC	System organ class
SWM	Spatial Working Memory
TEAE	Treatment-emergent adverse event
TG	Triglyceride
Total-C	Total cholesterol
TSH	Thyroid-stimulating hormone
ULN	Upper limit of normal
WBC	White blood cell

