5.6.1.2. Sensitivity to the Handling of Missing Data

Sensitivity analyses will be conducted to assess the robustness of primary analysis with regards to handling of missing data (3).

Visual examination:

- In order to explore the missing data pattern, post-baseline SWM strategy z-score observations during the TEAE period (in the primary safety population) will be described according to the following groups:
 - SWM strategy z-score available at week 96 (i.e. primary endpoint available),
 - SWM strategy z-score available at week 72 but missing at week 96,
 - SWM strategy z-score available at week 48 but missing from week 72,
 - SWM strategy z-score available at week 24 but missing from week 48,
 - SWM strategy z-score missing from week 24.

A graph of mean SWM strategy z-score (respectively change from baseline in SWM strategy z-score) \pm SE at baseline, and weeks 8, 12, 24, 48, 72, and week 96 will be provided by missing data pattern, for each treatment group.

- In the primary safety population, demographic and baseline characteristics will be described within the missing data pattern number 1 versus the pooled others. P-values from Chi-square test for categorical data and from asymptotic one-way ANOVA test for Wilcoxon scores (Kruskal-Wallis test) for continuous data, will be also provided, for descriptive purposes.

Multiple Imputations:

In addition to the MMRM method, the multiple imputation method (see Appendix 10.5 for more details) will be used to address missing values, in the primary safety population, followed by the testing of treatment arms using an analysis of covariance (ANCOVA) model, with the intent to evaluate the robustness of the primary analysis using a different statistical method.

Missing data from the primary safety population will be imputed 100 times to generate 100 complete data sets, using the MI SAS procedure (using Markov Chain Monte Carlo). The

percent change from baseline at week 96 will be then derived from observed and imputed SWM strategy z-score at this time point. The 100 complete data sets will be then analyzed using an ANCOVA model with treatment group and randomization strata (as per IVRS/IWRS) as fixed effects, and the baseline SWM strategy z-score as continuous covariate, and the MIANALYZE procedure will be used to generate valid statistical inferences by combining results from the 100 analyses using Rubin's formulae (4).

Pattern mixture model:

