10.5. Detailed Description of the Multiple Imputation Procedure

The following is a detailed description of the multiple imputation procedure which will be used for sensitivity analysis of primary endpoint as well as the analysis of the secondary endpoints.

In general, the missing pattern is anticipated to be not monotone, a two-step approach will be used:

- Step 1: the MCMC method will be used in conjunction with the IMPUTE=MONOTONE option to create an imputed data set with a monotone missing pattern.

- Step 2: Using the monotone data set from step 1, missing data will be imputed using the regression method.

The imputation model for step 1 will include the treatment group and the values of the analyzed parameter at baseline and planned time-points up to week 96.

The imputation model for step 2 will include the same variables as in step 1 with the following additional variables:

- the randomization strata (age and statin use strata);
- age, BMI, and gender (age and BMI included as continuous variables).

Non-continuous variables included in the imputer's model (i.e., treatment group, randomization strata and gender) are not expected to be missing.

In addition, for continuous efficacy variables anticipated to have a non-normal distribution (i.e. TG and Lp(a)), data will be log-transformed before imputation process and then back-transformed to create the imputed data sets using the TRANSFORM statement of SAS MI procedure.

For variables other than those continuous efficacy variables anticipated to have a non-normal distribution (i.e. TG and Lp(a)), for each simulation leading to negative imputed value, another value will be redrawn using MINIMUM option of MI SAS procedure.

The number of imputations (100) will be informally verified by replicating sets of 100 imputations and checking whether the combined results are stable. If not stable, the number of imputations will be increased and informally checked as above, and thus continued until stable estimates are obtained.

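### The SAP leaves the screening MoCA and GDS-S totals out of the baseline list, the completer comparison and the imputation model, a minor omission that costs nothing to repair

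*SAP*

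**What the plan says.** Protocol 7.6.1 groups several screening procedures under one sentence of purpose: "GDS-S and MoCA, and the Motor Screening Task will be performed for the purpose of determining study eligibility or characterizing the baseline population". Both scores are exclusion thresholds in protocol 4.2.2: "cognitive impairment (<26 score of the Montreal Cognitive Assessment [MoCA", and 11 or more for the "score of the Geriatric Depression Scale short form". Every eligible randomised patient should therefore have both totals, with MoCA between 26 and 30 and GDS-S between 0 and 10.

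Protocol 6.1 describes baseline characteristics as standard demography plus "disease characteristics including prior medication history related to LMT, and medical history". It names neither score.

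In the SAP, MoCA appears once, in the abbreviation list ("Montreal Cognitive Assessment"), and GDS-S does not appear. SAP 4.1 lists BMI, tobacco, alcohol, hs-CRP and hepatitis serology, but neither score. For variables outside the list it says "All baseline safety and efficacy parameters (apart from those listed below) are presented along with the summary statistics in the safety and efficacy sections".

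Two missing-data analyses depend on these choices:
- SAP 5.6.1.2: "demographic and baseline characteristics will be described within the missing data pattern number 1 versus the pooled others", where pattern 1 is the group with a week 96 score.
- SAP 10.5: imputation step 1 uses treatment group and the analysed score at baseline and at each visit. Step 2 adds the randomisation strata and "age, BMI, and gender (age and BMI included as continuous variables").

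**The concern.** The only primary endpoint is a cognitive score, and the protocol screens on mood and global cognition. As planned, the report would not show whether the arms, or patients with and without week 96 data, were alike on either measure.

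The multiple imputation is meant to test the primary result. It shares the MMRM's missing-at-random assumption and most of its variables, so much of what it can add comes from auxiliary predictors of dropout and outcome. The plan adds continuous age, BMI and gender, and leaves out two complete screening measures that lie close to the endpoint. If mood or global cognition predicts both dropout and later scores, and does so differently by arm, the imputed difference keeps a bias that the completer comparison would not reveal.

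**Working it through.** **The plan's own figures.** Inputs from SAP 2.2: margin 0.2, SD 1.0, true difference 0, one-sided 0.025, power 95%.
- Normal approximation: n = 2(1.960 + 1.645)² / 0.2² = 2 × 12.996 / 0.04 = 649.8, so 650 per arm. The noncentral-t calculation gives 651 (power 95.01%; 94.98% at 650), as stated.
- Retention: 0.80 × 0.75 = 0.60, and 651 / 0.60 = 1085, as stated.
- Planned share of randomised patients without week 96 data: 1 − 0.60 = 0.40, or 1085 − 651 = 434 per arm. This is an upper figure for the imputation. The primary safety population (SAP 3.1.2) requires at least one SWM strategy score in the treatment-emergent period, so patients with none are not imputed.

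**Where the two scores could enter.** They are not in SAP 4.1, not defined as variables in 4.6 to 4.9, and not in the 10.5 model. The MMRM, the subgroup analyses and the pattern-mixture model do not use them either. Baseline SWM strategy is in imputation step 1, and its mean is plotted by missing-data pattern and arm.

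**Size by formula (b, d and the lower f are assumed).** Bias in the week 96 difference is roughly f × b × d:
- f is the missing fraction.
- b is the slope of the week 96 z-score on the omitted score, given what is already in the model.
- d is the between-arm difference in that score, in SD, among patients with missing data.

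| f | b | d | bias (z) |
|---|---|---|---|
| 0.40 | 0.05 | 0.10 | 0.002 |
| 0.40 | 0.20 | 0.25 | 0.020 |
| 0.40 | 0.30 | 0.50 | 0.060 |
| 0.20 | 0.05 | 0.10 | 0.001 |
| 0.20 | 0.30 | 0.50 | 0.030 |
| any | any | 0 | 0 |

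**Size by simulation (all relations assumed).** 200,000 patients per arm; trait variance 0.5; GDS-S correlated 0.15 with baseline SWM; retention 0.60. GDS-S raises dropout in the Praluent arm only. Imputation is by sequential regression within arm. Lower scores are better, so a negative bias favours Praluent.

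| Effect of 1 SD GDS-S on week 96 z | Dropout log-odds per SD | Bias without GDS-S |
|---|---|---|
| 0.1 | 0.3 | −0.016 |
| 0.1 | 0.5 | −0.027 |
| 0.2 | 0.3 | −0.032 |
| 0.2 | 0.5 | −0.047 |

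With GDS-S in the model and all patients imputed, −0.003 to +0.001 remains.

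In the primary safety population the gain is smaller, because selection into that population has already happened. With dropout spread evenly within each year, the bias without GDS-S is −0.018 to −0.049 when all patients are imputed. In the primary safety population, −0.005 to −0.016 remains after adding GDS-S. A repeat gave −0.02 to −0.05 without it and −0.008 to −0.016 remaining. Setting the ends of the ranges against each other, 0.005/0.018 = 28% to 0.008/0.02 = 40% is left, so about two thirds is removed.

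Placing the dropout relation in the placebo arm reverses the sign. The same relation in both arms gives about zero. MoCA was not simulated.

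**The case against.** The strongest reply is that nothing here breaks the protocol. A reader might infer that the SAP contradicts protocol 7.6.1. It does not: that sentence gives eligibility or baseline description as alternative purposes for a list that also includes HIV and pregnancy testing, and protocol 6.1 names neither score. That stands.

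A reader might also infer that the plan ignores baseline cognition. It does not. The endpoint's own baseline and its later values are in the imputation model, baseline and baseline-by-time are in the MMRM, and baseline SWM is plotted by pattern. What is missing is MoCA, and mood altogether. The entry cuts narrow both scores, which may weaken what they could add.

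The bias needs a relation to dropout that differs by arm. Nothing in the documents of this double-blind trial supports one, and its direction is a free choice. The plan also does not rest on missing-at-random alone, since SAP 10.6 specifies a pattern-mixture model. Both points stand, and they limit the size of the concern.

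They do not answer the gap in the baseline table and the completer comparison, which needs no simulation to see. The pattern-mixture model does not use the scores either.

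**Conclusion.** The omission is confirmed, and it is minor. Including the two scores would make missing-at-random more plausible in the multiple-imputation sensitivity analysis and would make the completer comparison more informative for a cognitive endpoint.

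Under the assumed arm-specific dropout, the effect on that analysis is about 0.02 to 0.05 z in either direction, or 10% to 25% of the 0.2 margin (0.02/0.2 and 0.05/0.2). About two thirds of it is recoverable in the primary safety population. These sizes depend on assumed slopes and dropout relations. They are computed for GDS-S only; the case for MoCA rests on the reasoning alone.

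A reader might infer that the gap tilts the trial toward declaring non-inferiority. The documents do not support that. Non-inferiority is decided by the MMRM in SAP 5.6.1, which this change leaves alone, and the direction of any bias is unknown. Even 0.05 would take a true difference of 0.3, the lowest the plan calls possibly relevant, only to 0.25, still above the margin.

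**What to change.** - SAP 4.1: add MoCA total and GDS-S total, as continuous variables, to the baseline characteristics.
- SAP 5.6.1.2: this carries them into the comparison of pattern 1 with the other patterns. State that the comparison is also shown by treatment arm, since only an arm-specific pattern biases the difference.
- SAP 10.5, step 2: add both totals as continuous variables for the cognitive endpoint only, not for the lipid endpoints that share the procedure.

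The cost is a few words. The data are already collected and should be complete, because both scores decide eligibility. SAP section 1 allows revision before database lock. The primary MMRM, the margin, and the 651 and 1085 per arm do not change.

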4.2. Medical History and Disease Characteristics

As applicable, patient medical history, pre-listed or not in the e-CRF, will be dictionary coded by primary system organ class and preferred term using the Medical Dictionary for Regulatory Activities (MedDRA), specifically the MedDRA version in effect at the time of database lock for the analysis. Medical history of interest will be assessed through cardiovascular history and risk factors (dedicated and pre-listed e-CRF variables of acute myocardial infarction, silent myocardial infarction, etc., with outcome of occurred/not occurred), subject medical allergic history (dedicated and pre-listed e-CRF variables of allergic rhinitis, chronic sinusitis, etc., with outcome of occurred/not occurred), and family medical allergic history (dedicated and pre-listed e-CRF variables of allergic rhinitis, chronic sinusitis, etc., with outcome of occurred/not occurred). Additional other medical history (i.e., not already collected in the pre-printed e-CRFs) and surgical history will also be coded and reported.

Medical history of specific interest includes:

- Coronary heart disease (CHD)
- CHD risk equivalents

- Cardiovascular (CV) risk factors other than hypercholesterolemia (hypertension, type 2 diabetes, type 1 diabetes, family history of premature CHD). Smoking status will be summarized separately.
- Family history of type 2 diabetes
- Patient's allergies (described using all pre-printed terms collected in the medical allergic history e-CRF page).

Further for medical history variables, CHD, CHD risk equivalents, and CV risk factors are defined below, and will be based on items or combinations of items pre-listed in the dedicated medical history e-CRF page (unless otherwise specified). Patient status for primary and secondary CVD prevention is also defined below.

CHD (regardless if it is ongoing or not) is defined as at least one of the following events:

- Acute myocardial infarction
- Silent myocardial infarction
- Unstable angina
- Coronary revascularization procedure
- Other clinically significant CHD diagnosed by invasive or non-invasive testing

CHD risk equivalent (regardless if it is ongoing or not) is defined as at least one of the following events:

- Peripheral arterial disease: See definition below.
- Ischemic stroke
- Chronic kidney disease
- Known history of diabetes mellitus (type 1 or 2) AND 2 or more additional risk factors among:
 - History of ankle-brachial index ≤ 0.90
 - History of hypertension
 - History of microalbuminuria or macroalbuminuria or dipstick urinalysis at screening (week-2) with $>2+$ protein
 - History of pre-proliferative or proliferative diabetic retinopathy or laser treatment for diabetic retinopathy

- Known family history of premature CHD

As listed above, “Peripheral arterial disease” history is defined as follows, using combinations of the corresponding pre-listed medical history items of the e-CRF page “Cardiovascular history and cardiovascular risk factors”:

- Intermittent claudication (linked to PAD) TOGETHER WITH ankle-brachial index ≤ 0.90 ;

Or

- Intermittent claudication (linked to PAD) TOGETHER WITH peripheral revascularization procedure (angioplasty, stenting) for PAD or peripheral revascularization surgery (arterial bypass) for PAD;

Or

- Critical limb ischemia TOGETHER WITH peripheral revascularization procedure (angioplasty, stenting) for PAD or thrombolysis for PAD or peripheral revascularization surgery (arterial bypass) for PAD.

Secondary CVD prevention is defined as patients with any of the following history of CVD (other patients will be classified as primary CVD prevention):

- History of CHD (as defined above)
- History of ischemic stroke
- History of PAD with severity criteria defined as one of the following events:
 - Intermittent claudication and ankle brachial index ≤ 0.90
 - Peripheral revascularization procedure (angioplasty, stenting) for PAD
 - Thrombolysis for PAD
 - Peripheral revascularization surgery (arterial bypass) for PAD
 - Critical limb ischemia

CV Risk Factors are defined for this study as high risk and very high risk below.

- Very high CV risk patients are defined as patients with CHD or CHD risk equivalents (ASCVD).
- High CV risk patients are defined as all other patients.

Hyperlipoproteinemia disease history will be assessed through diagnosis of HeFH, time from diagnosis to study randomization (years), confirmation of diagnosis (genotyping [Yes/No], clinical diagnosis [Yes/No], lipid modifying therapies history and received at randomization as detailed below.

- Lipid modifying therapy history, as reported in the “History of Hypercholesterolemia/Statin Use” e-CRF page
 - Type of lipid-modifying therapy taken at screening (statin, fibrates, bile acid sequestrant, cholesterol absorption inhibitor, nicotinic acid and derivates, omega 3 fatty acids ≥ 1000 mg/day, other).
 - Number of patients at screening on a maximal tolerated dose of statin. For those not on statin or not taking the maximum tolerated dose, reason for not statin or not taking a maximum tolerated dose.
 - Number of patients with a history of down-titration of statin dose due to tolerability issues
 - Number of patients with a history of changing to a different statin due to tolerability issues

Lipid modifying therapies received at randomization will be derived from the prior and concomitant medication e-CRF pages by selecting medications with the type of lipid lowering medication tick box checked (“Statin” or “Other lipid modifying therapy”).

- Background lipid modifying therapy at randomization as reported in the dedicated prior and concomitant medication e-CRF pages
 - Number of patients taking atorvastatin 40 to 80 mg, rosuvastatin 20 to 40 mg daily
 - Atorvastatin daily dose in mg (10, 20, 40, 80, Other)
 - Rosuvastatin daily dose in mg (5, 10, 20, 40, Other)
 - Simvastatin daily dose in mg (10, 20, 40, 80, Other)
 - Other statins
 - Any LMT other than statins
 - Any LMT other than nutraceuticals (by chemical class and drug name)
 - Nutraceuticals (Omega 3 fatty acids (<1000 mg/day), Phytosterols, Psyllium/plantago, Policosanol, Other nutraceuticals)

Details (i.e. statin names, doses) for patients who had received at least 2 statins the day of randomization will be listed.

Statin use (no statin, low lipophilicity of the concomitant statin, or high lipophilicity of the concomitant statin) as per IVRS and as per eCRF will be summarized together with other baseline characteristics (Section 4.1).

